Phase 1, expected to last three months, involves the participation of 7 centers proposing the project and aims to structure the dataset and data entry methods. Actions will also be implemented for dissemination of the project by trying to recruit centers distributed across the national territory. Estimated start date 01/03/2023.

In phase 2, the project expands to the centers that wish to join, and this protocol will be fully operational.

The duration of phase 2 is two years and six months, presumably starting from 01/06/2023. Patient enrollment at each center will begin at different times depending on the rollout of the registry and local ethics committee approval. It is likely that the first patient will be prospectively enrolled in 01/06/2023. The last patient will be enrolled by 01/03/2025 and it will be possible to enter data and follow-up until 01/09/2025. The results of this study will be available by 01/12/2025.

Once the patient has been enrolled, it will be possible to trace the patient's personal file and update it at each follow-up until the end of enrollment.

In phase 3, SIAARTI will promote the register at the institutions for the establishment of a national register compliant with the DECREE OF THE PRESIDENT OF THE COUNCIL OF MINISTERS 3 March 2017 "Identification of surveillance systems and registers of mortality, tumors and other pathologies. (17A03142) (GU General Series n.109 of 12-05-2017)"

Setting

The study aims to collect demographic and clinical data from patients belonging to pain therapy centers recognized at the regional level and belonging to the pain therapy networks established in compliance with law 38/2010 and according to the Agreement between the Government and the Regions of 25 July 2012.

Patients will be registered regardless of the access modality (outpatient or hospitalization) and will be characterized by pathology and treatments performed. The participation of centers for the treatment of pediatric pain is expected. Data relating to patients under the age of 18 will be analyzed separately.

The database aims to follow the patients enrolled according to a code that makes them anonymous.

Participating Centers

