Once enrolled, the patient will be followed prospectively until the end of enrollment. At each visit it will be possible to retrieve the patient's chart and fill in the data relating to the intensity of pain and the treatments undertaken. It will also be possible to modify or add an etiological diagnosis in forms of secondary chronic pain. There is no limit to the number of follow-ups for each patient as long as the database is active (3 months from the date of enrollment of the last patient, considering a 12-month active enrollment expected for this study).

Data gathered

The activities of the registry do not replace routine diagnostic tests or visits to your doctor. The data collected by the registry will include relevant demographic data of the patient, comorbidities, the duration of the pain (> 5 years; from 1 to 5 years; from 1 year to 6 months; from 3 to 6 months), the type of pain, the location of the pain, the intensity of the pain (Brief Pain Inventory- Severity (BPI-S) and pain interference in daily activities (Brief Pain Inventory- Interference (BPI-I), treatments received (categorized according to pharmacological therapy, infiltrative therapy, ablative or neuromodulatory therapy, implants), the tests conducted, the number of other medical specialists contacted for the pathology being studied, the professional who sent it to the center. Specifically, the data collected is shown in Attachment 1
In particular, patients will be characterized by:

Type of pain (chronic primary or chronic secondary according to the scheme proposed by IASP)

Location of pain according to the following scheme (multiple options are possible)

- Lower back pain
- Thoracic
- Upper arts
- Lower limbs
- Head/Neck
- Pelvis

Pain Intensity

Brief Pain Inventory-Severity (BPI-S)

Interference with daily activities

Brief Pain Inventory-Interference (BPI-I)

Clinical information related to the pathology

Therapy
Pharmacological
Infiltrative
Implantable

Data collection methods and anonymization

The data collected will be used for scientific and epidemiological purposes. Each data will be created by a participating center and recorded on the SIAARTI Servers via a web application using the RedCap® data management software.

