6. ENDPOINT

Primary Endpoint

The number of patients referring to the centers, the type of pain, the proportion of patients who reach the clinically significant outcome, the type of therapies prescribed (pharmacological, neuromodulatory or implanted) necessary to achieve the outcome and the number of accesses and the Time in which a clinically significant improvement will be achieved (Change in BPI-s or BPI-I; a reduction of > 30% is considered clinically significant and a reduction of > 50% is considered optimal, the data will be evaluated for each Item).

Secondary Endpoint

1. The effectiveness of the treatments will be described in terms of
 - a. Change in pain intensity according to the Brief Pain Inventory-Severity questionnaire (BPI-S) A reduction of > 30% is considered clinically significant and optimal a reduction > of 50% the data will be evaluated for each Item)
 - b. b. Change in pain interference on daily activities according to the Brief Pain Inventory-Interference questionnaire (BPI-I). A reduction of > 30% is considered clinically significant and a reduction of > 50% is considered optimal; the data will be evaluated for each item)
2. Proportion of patients achieving clinically significant outcomes in relation to baseline characteristics and specific treatments performed and their intermediate surrogate outcomes in relation to specific patterns.
3. Resources used: Number of visits to the center for each patient in a year; Number of ordinary or day hospitalizations for each patient in a year.
4. The clinical variables relevant to the outcome will be described (e.g. type of pain, comorbidities, the time between treatment and clinically significant improvement, type of therapy undertaken - pharmacological, invasive, implant-based)

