8. STATISTICAL ANALYSIS

All enrolled patients registered in the registry will be included in the analyses. A descriptive analysis will be performed on the collected data. In general, qualitative variables will be described using frequency distributions; the quantitative variables will be described by mean and standard deviation if normally distributed, and by median and interquartile range if asymmetrically distributed. As appropriate, statistical tests will be used for exploratory purposes. Treatment effects (Change in BPI-S and BPI-I scores) will be calculated as the ratio of the difference between baseline and follow-up scores to the baseline score. If the data allow it, inferential analysis will be applied on quantitative data (such as: comparison of Student's t means, Fisher's F, etc.), or on qualitative data (such as: chi square, odds ratio, Mann Whitney U, etc.). The prevalence of the different pathologies and the related confidence intervals will be estimated. Detailed statistical analysis plans will be set up in future research protocols that will use this database as a source of data.

Sample Size

Since this is an observational registry, no prior sample size calculation is required. Considering an expected participation of 12 centers, an estimate of 2500 patients included appears reasonable.

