 - OTHER
 - CENTRAL
 - POST-ISCHEMIC
 - SM
 - TRIGEMINAL
 - NEURODEGENERATIVE DISEASES
 - HEADACHE OR OROFACIAL PAIN
 - VISCERAL
 - SKELETAL MUSCLE
 - LOW-BACK-PAIN
 - OTHER

AREA OF PAIN

- ◇ LOWER BACK PAIN

- ◇ THORACIC
- ◇ UPPER LIMBS
- ◇ LOWER LIMBS
- ◇ HEAD/NECK
- ◇ PELVIS

PAIN INTENSITY AND INTERFERENCE

- ◇ BPI-S

WORST PAIN IN THE LAST 24 HOURS

• 1 • 2 • 3 • 4 • 5 • 6 • 7 • 8 • 9 • 10

LEAST PAIN IN THE LAST 24 HOURS

• 1 • 2 • 3 • 4 • 5 • 6 • 7 • 8 • 9 • 10

AVERAGE PAIN IN THE LAST 24 HOURS

• 1 • 2 • 3 • 4 • 5 • 6 • 7 • 8 • 9 • 10

CURRENT PAIN

• 1 • 2 • 3 • 4 • 5 • 6 • 7 • 8 • 9 • 10

HOW MUCH RELIEF HAVE YOU HAD FROM THE THERAPY (%)

• 10 • 20 • 30 • 40 • 50 • 60 • 70 • 80 • 90 • 100

BPI-I (PAIN INTERFERENCE ON)

ACTIVITY IN GENERAL

• 0 • 1 • 2 • 3 • 4 • 5 • 6 • 7 • 8 • 9 • 10

MOOD

• 1 • 2 • 3 • 4 • 5 • 6 • 7 • 8 • 9 • 10

ABILITY TO WALK

• 1 • 2 • 3 • 4 • 5 • 6 • 7 • 8 • 9 • 10

NORMAL WORKING ABILITY (both at home and outside)

• 1 • 2 • 3 • 4 • 5 • 6 • 7 • 8 • 9 • 10

RELATIONSHIPS WITH OTHER PEOPLE

• 1 • 2 • 3 • 4 • 5 • 6 • 7 • 8 • 9 • 10

SLEEP

• 1 • 2 • 3 • 4 • 5 • 6 • 7 • 8 • 9 • 10

PLEASURE OF LIVING

• 1 • 2 • 3 • 4 • 5 • 6 • 7 • 8 • 9 • 10 • 1 • 2 • 3 • 4 • 5 • 6 • 7 • 8 • 9 • 10

REQUESTED EXAMS

- ◇ INSTRUMENTAL EXAMS
 - XRAY
 - MRI
 - SCINTIGRAPHY
 - EMG/ENG
 - OTHER
- ◇ LABORATORY EXAMS

COMPLETED EXAMS

- CLINICAL EXAMINATION OF SENSITIVITY
- QST-TEST
- DIAGNOSTIC BLOCK

LEVEL 3: THERAPY

PHARMACOLOGICAL THERAPY

- ◇ SNRI
- ◇ GABAPENTINOIDS
- ◇ TRICICLICS
- ◇ OPIOIDS
 - TRAMADOL
 - CODEINE/PARACETAMOL
 - OXYCODONE/PARACETAMOL
 - MORPHINE SR
 - MORPHINE IR
 - OXYCODONE
 - OXYCODONE/NALOXONE
 - HYDROMORPHONE
 - TAPENTADOL
 - TRANSDERMAL FENTANYL
 - TRANSMUCOSAL FENTANYL
 - BUPRENORPHINE
 - METHADONE

- ◇ NSAIDs
 - AS NEEDED
 - INTERVALS/REGULARLY (indicate how many days)
- ◇ COXIB
 - AS NEEDED
 - INTERVALS/REGULARLY (indicate how many days)
- ◇ PARACETAMOL
- ◇ OTHER

INFILTRATIVE THERAPY

- ◇ EPIDURAL
- ◇ INTRA-ARTICULAR (SHOULDER, KNEE, ANKLE, HIP, ECC)
- ◇ SPINAL FACET JOINTS
- ◇ SACRO-ILIAC
- ◇ PERIPHERAL NERVE

NEUROMODULATORY/NEUROABLATIVE THERAPY

- ◇ GANGLIAR RADIOFREQUENCY
- ◇ RADIOFREQUENCY OF PERIPHERAL NERVES
- ◇ CRIOAMODULATION
- ◇ EPIDUROLYSIS
- ◇ EPIDUROSCOPY

IMPLANTS

- ◇ SCS NON-RECHARGABLE
 - CERVICAL
 - DORSAL
- ◇ SCS RECHARGABLE
 - CERVICAL
 - DORSAL
- ◇ STIMULATION OF PERIPHERAL NERVE
- ◇ GANGLIAR STIMULATION
- ◇ INTRATHECAL PUMP

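### Ten of the eleven BPI answer grids in Attachment 1 have no 0, so no pain or no interference cannot be recorded and per-item improvement is understated on mildly affected items

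*Protocol*

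**What the plan says.** Section 5 (Data gathered) makes the attachment the data specification: "Specifically, the data collected is shown in Attachment 1".

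In Attachment 1, Level 2, the grids are:

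- **BPI-S pain items** (worst, least, average, current): all four run 1–10, including "LEAST PAIN IN THE LAST 24 HOURS".
- **BPI-I items:** "ACTIVITY IN GENERAL" is printed as "0 • 1 • 2 • 3 • 4 • 5 • 6 • 7 • 8 • 9 • 10". Mood, walking, work, relationships, sleep and pleasure of living run 1–10.
- **Relief item**, "HOW MUCH RELIEF HAVE YOU HAD FROM THE THERAPY": the grid runs 10–100%, with no 0.

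Section 6 sets a reduction above 30% as clinically significant and above 50% as optimal, in the primary endpoint and in secondary endpoint 1, and adds that "the data will be evaluated for each Item". Section 8 states that the change in BPI-S and BPI-I "will be calculated as the ratio of the difference between baseline and follow-up scores to the baseline score". No section gives another way to record 0 or rescales the scores.

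**The concern.** The one item printed with a 0 shows that the protocol itself treats 0 as a valid answer. On the other ten, the best possible outcome has no box to tick. A center must then either enter 1 or leave the item blank.

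If it enters 1, the reduction is understated, and on items that start low the patient can fail a threshold that was truly met. If it leaves the item blank, the best outcomes become missing data. Neither can be repaired in the analysis, because a 0 entered as 1 cannot be told from a real 1. The general activity item would also sit on a different scale from the other ten, which weakens comparison of change between items. Because evaluation is per item, no composite score dilutes the effect.

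**Working it through.** The protocol gives no figure on this point to reproduce. The check has three steps.

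**1. Count.** Four severity items plus seven interference items make 11. Grids without a 0: 4 + 6 = 10.

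**2. Exact arithmetic from the protocol's own formula.** Section 8 gives reduction = (b − f)/b, with baseline b and follow-up f. With lowest recordable f = 1, the maximum is (b − 1)/b. With f = 0 it would be 100%. The shortfall for a patient truly at 0 is 100/b percentage points.

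| Baseline b | Largest recordable reduction | Above 30% reachable? | Above 50% reachable? | Shortfall (points) |
|---|---|---|---|---|
| 1 | 0% | no | no | 100 |
| 2 | 50.0% | yes | no (50 is not above 50) | 50 |
| 3 | 66.7% | yes | yes | 33.3 |
| 5 | 80.0% | yes | yes | 20 |
| 10 | 90.0% | yes | yes | 10 |

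Enumerating every pair with b from 1 to 10 and f from 0 to 10, recoding 0 as 1 changes the >30% class only for (b, f) = (1, 0), and the >50% class only for (1, 0) and (2, 0).

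**3. Illustration of the effect on response proportions.** All inputs are assumptions, since the protocol gives none: SD 2.5 at both times, baseline–follow-up correlation 0.64, mean fall 1.5 to 2.0 points, bivariate normal scores rounded and clipped to 0–10, baseline above 0, no NRS restriction, 2,000,000 pairs per setting. Each range below covers the two falls.

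| Item baseline mean | Above 50%, true scores | Above 50%, 0 coded as 1 | Loss in above 30% (points) |
|---|---|---|---|
| 3 | 43–53% | 28–35% | 8–9 |
| 4 | 34–44% | 26–33% | 4–5 |
| 5 | 26–35% | 22–29% | 2 |
| 6 | loss about 2 points | | 1 or less |
| 7 | loss about 1 point | | 1 or less |

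Restricted to item baselines of 5 or more (mean 6, fall 2), both proportions are unchanged, at 23.7% for >50% and 53.4% for >30%.

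If zeros are left blank instead, 10–34% of follow-up scores are missing at means 3–5, and the >50% proportion among the rest is 18–29%. With baseline 5 or more (mean 6, fall 2), 2.6% are missing and the >50% proportion falls from 23.7% to 21.6%.

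On the relief item, a patient with no relief who is coded 10% is recorded 10 points too high.

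**The case against.** - **It may be a slip in the listing.** Attachment 1 is unpolished: some Italian text remains and the pleasure-of-living grid is printed twice. The REDCap screens are not shown and may already carry 0. This is possible. Loss of the 0 in reading the PDF is unlikely, since it survives on the general activity item in the same layout. If the screens are right, Attachment 1 is still wrong and must be made to match.
- **The effect on responder status is narrow.** This stands. If 0 is coded as 1, classes change only at item baselines 1 and 2, and Section 4 requires NRS > 4 at entry. But that criterion names no BPI item and sets no minimum for least pain or for any interference item, so these can start low.
- **The large losses rest on assumed inputs.** This also stands: the drop at mean 3 is an illustration. It also leaves out true baseline zeros, which the printed grid would record as 1 and keep as items that can never improve; including them would lower the recorded proportion further. The limits (b − 1)/b need no assumption.
- **Leaving zeros blank is conjecture.** No section describes it. It is one of only two things a center can do with the printed grid.
- **The relief item is printed under BPI-S.** Treating it as outside the change endpoints is an inference, since it records relief rather than a score that is meant to fall. The main point does not depend on it.
- **A rule for baseline 0 belongs in an analysis plan.** Often so, but the ratio fixed in Section 8 becomes undefined as soon as 0 is allowed, so the sentence belongs with it.

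**Conclusion.** The concern holds and should be fixed. As printed, ten of eleven items cannot record the absence of pain or interference. A reduction above 50% is then unreachable from item baselines 1 and 2, and one above 30% from baseline 1. The size of the change is understated by 100/b points for anyone who reaches 0. These results are exact and follow from Attachment 1 and Sections 6 and 8.

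The effect on reported proportions depends on how many items start low. Under the stated assumptions it is substantial at an item mean of 3, small at 6–7, and nil for responder status at baselines of 3 or more when 0 is coded as 1. The loss therefore falls mainly on least pain and mildly affected interference items. The registry is descriptive, so the harm is to the accuracy of the per-item proportions in the primary endpoint and secondary endpoint 1, not to a powered test.

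**What to change.** 1. In Attachment 1 and in REDCap, offer 0–10 for every BPI-S and BPI-I item and 0–100% for relief, before data entry starts. Phase 1, which "aims to structure the dataset and data entry methods", is the place to do it. If the REDCap screens already have 0, correct Attachment 1 to match.
2. Flag any records already entered on a grid without 0, so that they can be identified in the analysis.
3. Add one sentence to Section 8: compute the percentage change only for items with a baseline above 0, and report for each item how many patients had a baseline of 0.

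The cost is an edit to the answer options and one sentence of text. No extra patients, visits or staff are needed, and no clinical rule changes.

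### The relief-from-therapy item is listed under BPI-S, where the reduction rule read literally scores it backwards, and its scale has no 0%

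*Protocol*

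**What the plan says.** Attachment 1, Level 2, under pain intensity and interference, lists five entries between the BPI-S heading and the BPI-I heading. They are worst, least, average and current pain, each shown as 1 to 10, and then "HOW MUCH RELIEF HAVE YOU HAD FROM THE THERAPY", in per cent, with the options "10 • 20 • 30 • 40 • 50 • 60 • 70 • 80 • 90 • 100". Seven interference items follow under BPI-I.

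Section 6, Primary Endpoint, defines success on BPI-S or BPI-I item by item, in these terms: "a reduction of > 30% is considered clinically significant and a reduction of > 50% is considered optimal, the data will be evaluated for each". The rule returns for BPI-S alone under secondary endpoint 1a: "optimal a reduction > of 50% the data will be evaluated for each Item". The same secondary endpoint opens by naming the construct: "Change in pain intensity according to the Brief Pain Inventory-Severity questionnaire (BPI-S").

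Section 8 gives one formula for change in BPI-S and BPI-I scores, which "will be calculated as the ratio of the difference between baseline and follow-up scores to the baseline score". None of these places names the BPI-S items covered, leaves relief out, or reverses its sign.

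**The concern.** On the four pain items and the seven interference items a lower score is better, so a reduction is an improvement. On the relief item a higher score is better. A rule that counts reductions, applied to every item under BPI-S, gives the relief item the opposite of its intended meaning. An item-by-item table built on the literal text would hold one row whose responders are the patients reporting less benefit from treatment than before.

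There is also a fault of data capture. The lowest relief option is 10%, so a patient with no relief has no valid answer. A patient who has not yet received any therapy has no meaningful answer either. An entry of 10% for no relief cannot later be told apart from a true 10%, and a blank cannot be told apart from a missing answer.

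**Working it through.** **Inputs**
- Change formula (Section 8): change = (baseline - follow-up)/baseline.
- Cut-offs (Section 6): above 30% is clinically significant and above 50% is optimal, both as reductions and both strict.
- Relief scale (Attachment 1): 10 to 100 in steps of 10, higher is better.

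The protocol states no figure of its own on this point, so there is none to reproduce.

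**Single cases on the relief item**

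| Relief at baseline | Relief at follow-up | Change | Under the literal rule |
|---|---|---|---|
| 20 | 80 | (20-80)/20 = -300% | worsening |
| 10 | 100 | (10-100)/10 = -900% | worsening |
| 70 | 40 | (70-40)/70 = +42.9% | clinically significant |
| 80 | 40 | (80-40)/80 = +50.0% | clinically significant; not optimal, as the cut-off is strict |
| 80 | 30 | (80-30)/80 = +62.5% | optimal |
| 100 | 10 | (100-10)/100 = +90.0% | optimal |

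For comparison, a pain item falling from 8 to 4 gives (8-4)/8 = +50%, which is the intended direction.

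**All possible pairs.** Ten options at each of two visits give 10 × 10 = 100 pairs: 45 gains, 45 losses and 10 with no change. The rule is met at above 30% by 33 pairs and at above 50% by 20 pairs. Every one of these is a loss of relief, and none of the 45 gains qualifies. These are counts of score combinations, not forecasts of how many patients would show them. They establish only that the reversal is complete for this item.

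**Reach.** Four pain items, one relief item and seven interference items make 4 + 1 + 7 = 12, so 1 of 12 is affected.

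**Can the change be computed in practice?** Yes, for some patients. Attachment 1 requires the CRF at every visit or admission, and Section 5 allows enrolment at a check-up or during a hospital stay, so patients already under treatment can have a relief score at baseline.

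**Effect of adding a 0.** With a baseline of 0 the Section 8 ratio would divide by zero. A relief scale that can record no relief therefore cannot stay under that formula.

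**The case against.** The strongest defence is that the construct limits the rule. Secondary endpoint 1a speaks of change in pain intensity, and Section 5 describes BPI-S in the same way. Percentage relief is not pain intensity, so a careful analyst would probably leave it out. Attachment 1 is also a list of data gathered rather than a scoring manual. Its layout did not survive text extraction perfectly, and a statistical analysis plan that is not shown may name the scored items. This stands as a reason to think the reversal unintended. It does not remove the conflict: exclusion has to be inferred, while the per-item wording and the single formula point towards inclusion.

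A reader might infer that the primary endpoint will count patients whose treatment is failing as responders, or that the responder proportion is inflated by some amount. The documents do not support that. They define no BPI-S summary score and do not say how item results become a patient-level response, so no size can be given. Results shown item by item would leave the other 11 items untouched.

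A reader might also infer that first-visit patients in general lack a baseline on this item. That goes too far. The item asks about therapy without limiting it to the centre's own, and Attachment 1 lists referral by family doctors and other specialists, so some first-visit patients may already be on treatment. Only those not yet treated clearly lack a baseline.

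Finally, the missing 0 is not special to relief: in Attachment 1 only the general-activity item shows one. That makes it a separate question from direction, and it is no evidence for the reversal. It still matters here, because no later analysis can recover an answer that the form did not offer.

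**Conclusion.** The point holds in a limited form. Sections 6 and 8, applied literally to the Attachment 1 layout, reverse the meaning of one listed item out of 12. For that item the reversal is complete, while the other 11 run in the right direction. The conclusion assumes that the relief item belongs to BPI-S, as its position between the two headings indicates, and that each item means every item listed there. The pain-intensity wording makes it likely that the sponsor did not intend this, and the effect on the overall responder proportion cannot be quantified. The absence of a 0% option is a separate capture fault, on the assumption that the printed scale is the one in the electronic form. Both are worth correcting because the correction is cheap, and because Section 8 leaves detailed analysis plans to future protocols that will draw on this database and inherit its definitions.

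**What to change.** 1. In Section 6, state that the reduction rule covers only the four BPI-S pain items (worst, least, average and current) and the seven BPI-I items.
2. State that relief is reported separately, as its value at each visit and not as percentage change from baseline.
3. In Attachment 1 and the electronic form, add a 0% option to the relief item, and a not-applicable option where no therapy has yet been given.

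Moving the field out of the BPI-S block is optional once the first two statements are in place.

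The cost is a sentence or two in Section 6 and two added response options on one REDCap field. It adds no visit and no question for patients. Relief entries already made as 10% or left blank could not be reclassified afterwards, so the form should be changed as early as possible.

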4. STUDY POPULATION

The Registry data will be collected by the structures involved in the management of patients suffering from chronic pain, regardless of the cause. It is necessary to keep the inclusion criteria as broad as possible to obtain a real picture of clinical practice at a national level.

Inclusion criteria

- Subjects > 4 years old
- NRS > 4
- Diagnosis of Chronic Pain according to the IASP19 criteria
- Adherence through written informed consent to participate in the study

Exclusion criteria

- Patients suffering from psychiatric pathology or severe cognitive impairment for which the enrolling doctor does not believe it is useful for the purposes of the study
- Patients unable to sign the informed consent

Description of the pathologies being studied

Adult patients will be enrolled, diagnosed with Chronic Pain (pain lasting > 12 weeks), regardless of the etiology, modality, and age of onset.

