5. PROCEDURES EXPECTED AND INFORMATION COLLECTED

Enrollment procedure

Adult patients of both sexes who belong to pain therapy centers with a diagnosis of Chronic Pain (pain that lasts > 12 weeks), regardless of the etiology, modality and age of onset, will be considered eligible for enrollment.

It will be possible to enroll patients during their first visit (FIRST ANESTHESIOLOGICAL VISIT), or during a check-up visit (ANESTHESIOLOGICAL CHECK-UP VISIT) or during a scheduled hospitalization for pain procedures (ORDINARY OR DAY HOSPITAL ADMISSION)

Patients will be asked to join the study after having been informed in detail (also with the aid of a written information form) of the objectives of the project, as well as the methods with which these objectives will be pursued. Participants will be informed about the lack of informative feedback regarding the results of future clinical evaluations: the results of any research originating from the register, in fact, will not be delivered to the participants themselves. The subject who freely accepts will authorize the inclusion of their data in the project by signing the informed consent form of which they will receive a copy. It will also be clearly explained in the information sheet attached to the informed consent that each participant will have the possibility of withdrawing their participation from the study at any time, without providing any reason and without this jeopardizing the doctor-patient relationship with the specialists involved in the project.

Patients will be informed by the manager of the patient's pain center or the principal investigator for the center (assuming this is not the same individual).

The doctor will complete the electronic CRF after evaluating the patient and classifying him according to the criteria of the IASP (International Association for the Study of Pain) in terms of primary or secondary chronic pain. In the case of a patient enrolled during a check-up or during hospitalization, all data relating to the time in which the patient is in care at the center, the

invasive procedures previously undertaken, the drugs prescribed, will be collected. Retrospective data (only for patients already being treated at the center) will be collected according to a predefined group (e.g.: the patient has been in the care of the center for: > 5 years; from 1 to 5 years; from 1 year to 6 months; from 3 to 6 months; < 3 months).

[figure not shown]
Follow-up procedure

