12. ETHICAL CONSIDERATIONS

This observational study is designed and will be conducted according to the current protocol, in accordance with EU Directive 2001/20/EC relating to the implementation of the principles of good clinical practice in the conduct of clinical trials on medicinal products for human use, in accordance with the principles published in Good Clinical Practice (GCP) guidelines and in accordance with the Declaration of Helsinki on Ethical Principles for Medical Research Involving Human Subjects, adopted by the General Assembly of the World Medical Association (1996),

The investigator guarantees that personal patient data will be protected and processed in accordance with the General Data Protection Regulation (EU) 2016/679 (GDPR) on data protection and privacy.

ATTACHMENT 1

DATA GATHERED FOR EACH PATIENT

- ◇ CENTER CODE
- ◇ UNIQUE PATIENT CODE
- ◇ ACCESS METHOD (TO BE COMPLETED ONLY THE FIRST TIME FOR EACH PATIENT)
- ◇ DATE (the CRF must be filled in each time the patient has a visit/admission)
- ◇ SENT BY:
 - FAMILY DOCTOR
 - OTHER SPECIALIST
 - ADVICE FROM A RELATIVE/ACQUAINTANCE
 - WEB SEARCH
- ◇ REFERRAL METHOD (TO BE COMPLETED ONLY THE FIRST TIME FOR EACH PATIENT)
 - ◇ FIRST ANESTHESIOLOGICAL VISIT
 - ◇ ANESTHESIOLOGICAL CHECK-UP EXAMINATION
 - UNDER CARE AT THE CENTER FOR:
 - > 5 years;
 - from 1 to 5 years;
 - from 1 year to 6 months; or 3 to 6 months;
 - < 3 months
 - ◇ ORDINARY HOSPITALIZATION
 - IN EMPLOYMENT AT THE CENTER FOR:
 - > 5 years;
 - from 1 to 5 years;
 - from 1 year to 6 months; or 3 to 6 months;
 - < 3 months
 - ◇ DAY HOSPITALITY (DAY SURGERY OR DAY HOSPITAL)
 - IN EMPLOYMENT AT THE CENTER FOR:
 - > 5 years;
 - da 1 a 5 anni;
 - da 1 anno a 6 mesi; o da 3 a 6 mesi;
 - < 3 mesi

LEVEL 1: DEMOGRAPHICS

- ◇ AGE
- ◇ SEX
 - M
 - F

STATE/COUNTY OF RESIDENCE

SCHOOL LEVEL

- ◇ Not Known
- ◇ Grade School
- ◇ High School
- ◇ University

WORK

- ◇ WORKER
- ◇ UNEMPLOYED

COMORBIDITIES

- ◇ CARDIOVASCULAR
- ◇ DIABETES
- ◇ RESPIRATORY
- ◇ AUTOIMMUNITY
- ◇ CHRONIC INFLAMMATION
- ◇ OTHER

LEVEL 2: DIAGNOSIS

TYPE OF PAIN

- ◇ PRIMARY CHRONIC
 - CHRONIC WIDESPREAD PAIN
 - FIBROMYALGIA
 - OTHER
 - CRPS

- HEADACHE OR OROFACIAL PAIN
- MUSCULOSKELATAL
 - LOW-BACK PAIN
 - ALTRO
- ◇ SECONDARY CHRONIC
 - ONCOLOGICAL
 - POSTSURGICAL
 - LUMBAR
 - CERVICAL
 - BREAST
 - INGUINAL HERNIA
 - THORACOTOMY
 - OTHER
 - POST TRAUMATIC
 - CRPS
 - OTHER
 - NEUROPATHIC
 - PERIFERAL
 - POST-TRAUMATIC
 - DIABETIC
 - TRIGEMINAL
 - POST-HERPETIC

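### Attachment 1 has no valid WORK code for retired people, students, homemakers or young children, and no not-applicable answer on the BPI-I work item

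*Protocol*

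**What the plan says.** **The form.** Attachment 1 is headed "DATA GATHERED FOR EACH PATIENT" and has no branch by age. Under Demographics, WORK has two options, WORKER and UNEMPLOYED. The school-level field just above it does have an option for unknown; WORK has no comparable option.

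**The interference item.** The BPI-I block of Attachment 1 has seven items. One is "NORMAL WORKING ABILITY (both at home and outside". As printed it runs from 1 to 10, with no not-applicable choice.

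**The outcome rule.** Section 6, Primary Endpoint, uses change in BPI-S or BPI-I with cut-offs of more than 30% and more than 50% reduction, and adds that "the data will be evaluated for each Item". Section 8 defines change as baseline minus follow-up, divided by baseline.

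**Who is enrolled.** The protocol states this in two ways.
- Minors are in scope: the inclusion criterion in Section 4 is "Subjects > 4 years old". Section 3, Setting, says "The participation of centers for the treatment of pediatric pain is expected" and "Data relating to patients under the age of 18 will be analyzed separately". Section 7 provides for parental consent.
- Minors are not in scope: Section 4 also says "Adult patients will be enrolled, diagnosed with Chronic Pain", and the enrollment procedure in Section 5 begins "Adult patients of both sexes who belong to pain therapy centers".

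**The concern.** A two-way WORK field assumes that everyone is either in work or out of work and available for it. Retired people, students, homemakers and young children fit neither option. If they are coded as unemployed, that category becomes a mixture of unlike groups. If the field is left blank, the analyst cannot tell a question that did not apply from one that was overlooked. WORK is a baseline characteristic, and the second secondary endpoint relates response to baseline characteristics, so a tabulation of response by work status would be hard to interpret. No later analysis can separate groups that were recorded under one code.

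The BPI-I work item raises a narrower question. A young child may have no working ability to rate. If a number is entered only to complete the row, it still passes through the response rule, because each item is evaluated in its own right.

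**Working it through.** The protocol makes no sample size calculation and gives no figure for this point, so there is nothing to reproduce. The check compares the form with the population and endpoint sections and adds short arithmetic.

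**1. WORK codes against possible patients (Attachment 1)**

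| Patient | Valid code? |
|---|---|
| Employed adult | Yes, WORKER |
| Adult without a job and seeking one | Yes, UNEMPLOYED |
| Retired, student or homemaker | None |
| Young child (if minors are enrolled) | None |

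The third row does not depend on whether minors are enrolled. The fourth does.

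The number of patients in the third row is not given. As an assumption only, if 20 to 50% of patients were retired, students or homemakers, then of the roughly 2500 expected in Section 8 this would be 0.20 × 2500 = 500 to 0.50 × 2500 = 1250 without a valid code.

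**2. Share of the interference scale**

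The items are general activity, mood, walking, work, relationships, sleep and enjoyment of life: seven in all. The work item is 1/7 = 14.3% of them. This is a share of items; it is not a bias or a share of patients.

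**3. What a placeholder does under the response rule**

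Change = (baseline − follow-up) / baseline (Section 8). If the same placeholder w is entered at both visits:

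change = (w − w) / w = 0 / w = 0% for any w from 1 to 10.

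0% is below both cut-offs, so the patient counts as a non-responder on this item whatever happened to the pain.

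**4. Effect on that item's response rate**

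Let p be the share of the under-18 set to whom the item does not apply and who receive a constant placeholder, and r the response rate among the rest. The reported rate is (1 − p) × r, so it falls short of r by the proportion p. The protocol gives no value for p or for the number of minors. If not-applicable answers are recorded as such and left out of the denominator, the reported rate is r.

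**5. Effect on the other items**

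Each item is evaluated separately, so w appears in no other item's ratio. The other six results do not change.

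**The case against.** The strongest case against the point has five parts.

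- **No field is stated to be mandatory.** Attachment 1 asks for the form to be completed at each visit or admission, not for every field to be answered. One might infer that every child has to rate the work item and has to be coded as worker or unemployed; the text does not say so. This stands. What remains is that a blank has no recorded meaning.
- **The dataset is still to be shaped.** Phase 1 exists to structure the dataset and the entry methods, so response options may be settled there. This is fair. It makes the point a form correction with a natural date, not a fixed design error, but the list as printed still lacks the options.
- **The paediatric part may not arise.** If the adult-only statements in Sections 4 and 5 govern, no child meets the work item. This also stands, and the contradiction has to be resolved first. The gap for retired people, students and homemakers remains either way.
- **The item also covers activity at home.** Older children and adolescents may be able to answer it. One might infer that the paediatric interference outcome is invalid, or that an adult instrument is being misapplied. The protocol does not call the form an adult form; it only shows no paediatric version. The supportable description is inapplicable or ambiguous, most clearly for the youngest.
- **WORK is named in no endpoint.** Secondary endpoint 2 speaks only of baseline characteristics in general. Distortion of a named result is therefore not shown.

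A reader might also infer that the item dilutes a BPI-I total. For example, let six items each fall from 6 to 4 (33.3%) and the work item stay at w. A seven-item mean would fall by 12 / (36 + w): 32.4% at w = 1, 30.0% at w = 4 and 26.1% at w = 10, so from w = 4 the more-than-30% threshold would be missed. But the protocol defines no BPI-I total or mean. Section 8 speaks only of scores and Section 6 evaluates items, so this is not part of the finding. Recording whether the child or a parent answered would be a sensible addition, but its absence contradicts nothing in the protocol.

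**Conclusion.** The point holds as a minor data-capture defect. As printed, WORK has no valid code for retired people, students and homemakers of any age, nor for young children if they are enrolled. The BPI-I work item has no way to record that it does not apply. The reach is one demographic field and one of seven interference items. On that item, a constant placeholder turns an inapplicable answer into a non-response; the other six items are unaffected.

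The documents do not support a wider claim that the under-18 interference results as a whole are compromised. Any paediatric problem also stays out of the adult results, because under-18 data are analysed separately.

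The conclusion rests on three conditions: that Attachment 1 reflects the options in the electronic form, that some patients outside the two WORK categories are enrolled, and, for the BPI-I part only, that minors are enrolled and a placeholder is entered. The number of patients affected cannot be derived from the protocol. The point deserves attention despite its small size because the lost distinction cannot be restored at analysis.

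**What to change.** Before Phase 2 starts:

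1. Reconcile the statements on enrolling minors in Sections 3, 4, 5 and 7.
2. Add student, retired, homemaker and not-applicable options to WORK.
3. Add a not-applicable option to the BPI-I work item.
4. Add one sentence to Section 8: not-applicable answers to the work item are excluded from the denominator of that item's response rate, and their number is reported.

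The cost is a slightly longer form and a smaller denominator for one item, which is then not identical to the denominators of the other six.
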